In conclusion, when randomizing 180 subjects to Group U and 90 subjects each to Groups G&H and P, the study will have at least 90% power to establish efficacy of NT 201 using a hierarchical procedure for comparisons of proportions of GFL-, HFL-, and LCL-responders between Groups U and P. Assuming that about 15% of subjects will not complete the MP period, the proposed sample size will result in more than 150 completed subjects in Group U in this study. This number of completed patients in this study is considered sufficient to support the overall safety profile of NT 201 for simultaneous treatment of UFL.

4 Analysis Sets

The following analysis sets are defined for the statistical analysis of this study:

Safety Evaluation Set (SES)

The SES is the subset of all subjects who were exposed to study medication at least once. Subjects in the SES analyses will be analyzed as treated.

Note: In the definition of the SES above, "as treated" relates to actual study treatment in MP.

Full Analysis Set (FAS)

The FAS will consist of all randomized subjects. Subjects in FAS analyses will be analyzed as randomized.

Per Protocol Set (PPS)

The PPS is the subset of subjects in the FAS without major protocol deviations. Major protocol deviations will be defined during the blinded data review meeting.

Note: Subject **CCI** was randomized twice and only treated after second randomization. According to ITT principle treatment group from first randomization **CCI** will be used for analyses based on the FAS or PPS. Apart from random group assignment, no data recorded for **CCI** will be analyzed. Data recorded for **CCI** (second randomization) will be included in any statistical analyses.

5 Endpoints and Main Estimands for Analysis

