5.2.2 Secondary Safety Endpoints

- Incidence of related treatment-emergent adverse events (TEAEs) in MP.

- Incidence of related TEAEs in OLEX period

For the definition of TEAEs, see CCI

CCI

6 Statistical Analysis Methods

Continuous endpoints (values and changes from baseline/ cycle baseline, where applicable) will be summarized by number of subjects in the respective analysis set/ population (N), number of values analyzed (n), mean, standard deviation, median, quartiles, minimum, and maximum. If relevant, the number of values imputed due to missingness (nimp) will be reported for efficacy variables (see [Section 6.4.1](#)). Mean, quartiles, and median will be reported to one decimal place more than the data were collected, for the standard deviation two decimal places more will be displayed; for derived data, an adequate number of decimal places will be chosen.

For qualitative endpoints, absolute and percent frequencies (n, %) and, if applicable, shift tables will be displayed. Frequency tables will include the number of missing values, if applicable. Percentages will be calculated using the denominator of all subjects in a specified population or treatment group. The denominator will be specified in a footnote to the tables for clarification if not otherwise obvious. Percentages will be reported to one decimal place. In frequency tables based on observed cases, number of missing values will not be presented and percentages will be based on number of observed cases (Nobs).

If not otherwise specified, statistical tests will be conducted two-sided at type I error rate 5%. P-values will be reported to four decimal places (e.g., $p=0.0375$). P-values below 0.0001 will be presented as '<0.0001'. Confidence intervals (CIs) will be two-sided 95%.

In general, values obtained at Visit 2 are defined as the baseline values. Where data is not recorded at Visit 2, the last measurement before start of treatment is defined as baseline value. These values will be analyzed as baseline (i.e. baseline flag is 'yes' for last record with non-missing value before first treatment in Study Data Tabulation Model [SDTM]). For cycle 2 values obtained at Visit 8 and for cycle 3 values obtained at Visit 13 will be used as cycle baselines.

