6.2 Safety Endpoints

All safety analyses will be performed on the SES. All safety tables will be presented by actual treatment group (“Group P”, “Group U”, “Group G&H”) at V2 in MP. In TEAE tables for total OLEX period, Cycle 2, and Cycle 3, the column headers for these three treatment groups will be “MP Group P”, “MP Group U”, “MP Group G&H”. TEAE tables for MP will additionally include a “Total NT 201” column for which active treatment groups (Group U and Group G&H) will be pooled. TEAE tables for total OLEX period, Cycle 2, and Cycle 3 will present pooled results from all three treatment groups in the fourth column, which will be labeled “Total”. For TEAE analyses over total study period, the columns “MP Group P - MP”, “MP Group P - OLEX”, “MP Group U”, “MP Group G&H” and “MP Total NT 201” (“MP Group P – OLEX, MP”, “Group U” and “Group G&H” pooled) will be presented. In column “MP Group P - MP” only AEs which occurred during MP are counted, in column “MP Group P - OLEX” only AEs which occurred in OLEX period are counted.

All analyses of laboratory values from any timepoint (Screening V1 and end-of-study visit V17) will be performed by actual treatment group at V2 in MP and in total. All analyses of vital signs from any timepoint will be performed by actual treatment group at V2 in MP, Total NT 201 (labeled “MP Total NT 201” for analysis of vital signs from visits total OLEX period) and in total.

AEs will be coded according to the MedDRA version in effect at the time the database is closed. Only TEAEs will be analyzed, which are defined as AEs with onset or worsening on or after date of the first administration of investigational product (IP) up to and including end of study visit (V17). In case no end of study visit (V17) is performed, all AEs reported during a time period corresponding to the expected cycle length will be regarded as treatment-emergent. Further details for separation of TEAEs and non-TEAEs can be found in CC1. Non-TEAEs will be listed only.

All analyses of TEAEs will be based on the following time periods:

- Total study period
- MP (Cycle 1)
- Total OLEX period (Cycle 2 and Cycle 3)
- Cycle 2
- Cycle 3.

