TEAEs of the MP are defined as AEs with onset or worsening on or after date and time of the first administration of IP at V2 and before date and time of administration of IP in V8 (Cycle 2) or up to and including end of study visit (V17) in case of premature discontinuations prior to V8. For subjects who do not receive study treatment during OLEX period all AEs with onset or worsening on or after date and time of the first administration of IP up to and including end of study visit (V17) will be considered as TEAEs of MP. In case no end of study visit (V17) performed, all AEs with onset or worsening up to and including Day 120 of MP will be regarded as TEAEs of MP.

TEAEs of the total OLEX period are defined as AEs with onset or worsening on or after date and time of the first administration of IP during OLEX period at V8 and up to and end of study visit (V17) visit. In case no end of study visit (V17) is performed, all AEs with onset or worsening at or after date and time of the first administration of IP during OLEX period at V8 and up to and including Day 120 of last cycle will be regarded as TEAEs of OLEX. TEAEs of Cycle 2 are defined as AEs with onset or worsening on or after date and time of the first administration of IP at V8 and before date and time of administration of IP at V13 (Cycle 3) or up to and including end of study visit (V17) in case of premature discontinuations prior to V13 or in case no study treatment is

administered at V13. In case no end of study visit (V17) is performed, all AEs with onset or worsening at or after date and time of the first administration of IP at V8 and up to and including Day 120 of Cycle 2 will be regarded as TEAEs of Cycle 2. TEAEs of Cycle 3 are defined as AEs with onset or worsening on or after date and time of the first administration of IP at V13 and up to and including end of study visit (V17). In case no end of study visit (V17) is performed, all AEs with onset or worsening at or after date and time of the first administration of IP at V13 and up to and including Day 120 of Cycle 3 will be regarded as TEAEs of Cycle 3.

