For analysis over the total study period, the number of subjects in the SES will serve as the denominator for calculation of incidences. For the analyses by treatment cycle the denominator will be adjusted to all subjects being treated in that treatment cycle. For the analysis over the total OLEX period, the denominator for the incidences will be all subjects being treated at least once in total OLEX period.

If an AE worsens between start and end of this AE it will be considered as new AE starting with the date of worsening. In this case the imputation of end dates within episodes of the same AE will be done by setting the end date/end time to start date/start time of the consecutive worsening record.

For analysis, incompletely recorded or completely missing start of AEs will be estimated according rules laid down in **CCI**. End dates will not be imputed. In the AE listing, start date as recorded and as imputed for analysis will be displayed.

Calculation of time to onset/duration of AEs (days):

- Time to onset of an AE is defined as start date of AE - date of first administration of study drug in respective treatment cycle [+ 1 day for TEAEs]
- The duration of an AE will be calculated as stop date - onset date + 1 day.

If a subject has more than one intensity/ causal relationship to treatment/ outcome within a preferred term (PT) only the worst intensity/ causal relationship to treatment/ outcome will be considered for calculation of incidence rates in the frequency tables reporting incidences by intensity/ causal relationship to treatment/ outcome. Incidence of TEAEs related to COVID-19 disease and TEAEs related to COVID-19 vaccination will only be calculated overall. Thereby, TEAEs with missing relationship will be ignored but affected subjects will not be removed from the denominator. Also, for the analysis overall, i.e. for subjects with at least one TEAE, only the worst intensity/ causal relationship to treatment/ outcome category per subject will be counted for calculating incidence rates. The same applies to calculation of overall incidence of TEAEs related to COVID-19 disease and TEAEs related to COVID-19 vaccination.

The worst outcome is defined in the following order (worst outcome to best outcome):

- fatal
- unknown
- not recovered/not resolved
- recovering/resolving
- recovered/resolved with sequelae
- recovered/resolved

AEs coded as “Immunisation reaction” (preferred term) are defined as AEs related to COVID-19 vaccination.

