6.2.2 Secondary Safety Endpoints

Tables displaying incidences of related TEAEs will be provided by system organ class (SOC) and PT for time periods and with table columns as defined at beginning of [Section 6.2](#) above. Related TEAEs in MP and OLEX will also be listed.

CCI

CCI

CCI

CCI

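### In the total-study-period TEAE tables, the SES denominator does not fit the column that counts only Group P's OLEX events

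*SAP*

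**What the plan says.** SAP Section 6.2 presents safety tables by the treatment actually received at V2. For TEAE analyses over the total study period it sets five columns: *MP Group P - MP*, *MP Group P - OLEX*, *MP Group U*, *MP Group G&H* and a pooled *MP Total NT 201*. In the second of these, "only AEs which occurred in OLEX period are counted".

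The same section gives three denominator rules:

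- Total study period: "For analysis over the total study period, the number of subjects in the SES will serve as the denominator for calculation of incidences".
- By cycle: the subjects treated in that cycle.
- Total OLEX period: "the denominator for the incidences will be all subjects being treated at least once in total OLEX period".

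Section 6.2 also fixes what can count as an OLEX event: "TEAEs of the total OLEX period are defined as AEs with onset or worsening on or after date and time of the first administration". The injection meant there is the one given at V8, which opens the OLEX period. For anyone not injected in OLEX, every event goes to the MP: "For subjects who do not receive study treatment during OLEX period all AEs with onset or worsening" from the first injection onward is classed as a TEAE of the MP.

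The opening of SAP Section 6 supports reading the SES column by column: "Percentages will be calculated using the denominator of all subjects in a specified population or treatment group". SAP Section 4 defines the SES by a single exposure to study medication and ties the as-treated grouping to the MP treatment.

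SAP Section 6.2.2 carries the layout over to the secondary safety endpoint: "Tables displaying incidences of related TEAEs will be provided by system organ class (SOC) and PT for time periods and with table columns" taken from the start of Section 6.2.

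**The concern.** The column *MP Group P - OLEX* should show what happened to placebo subjects once they received NT 201. Under the stated rule its base is every subject given placebo at V2, including those who never received NT 201. These subjects cannot have an event in this column, because the SAP assigns all their events to the MP.

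The error runs in one direction only: it lowers a reported NT 201 incidence. That sits badly with the worst-case handling of missing intensity and missing causality elsewhere in Section 6.2. It also means that the same Group P events carry one percentage in the total-study tables and another in the total-OLEX tables, with nothing in the visible text to explain the difference. The pooled column *MP Total NT 201* takes in the same Group P OLEX experience and inherits a diluted form of the problem.

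No test, alpha allocation or sample size depends on these figures.

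**Working it through.** **Who can be counted.** Set side by side, the rules of Section 6.2 give, for a Group P subject treated in the MP:

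| | Injected at V8 | Never injected at V8 |
|---|---|---|
| Can enter the *MP Group P - OLEX* numerator | Yes | No (all events assigned to the MP) |
| In the total-study denominator (SES, by MP group) | Yes | Yes |
| In the total-OLEX denominator | Yes | No |

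The right-hand group is a foreseen one. Protocol Section 9.2 has subjects who do not meet the reinjection criteria leave the study.

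**Inputs.** Group U has 180 subjects and Groups G&H and P have 90 each (SAP Section 3). All 90 Group P subjects are assumed to be treated. The proportion *d* of Group P never treated in OLEX is not given. As a proxy I use the plan's figure for all groups, "Assuming that about 15% of subjects will not complete the MP period" (SAP Section 3), with 5% as a lower case.

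**The plan's own figure.** Group U completers at 15% non-completion: 180 × 0.85 = 153, which agrees with the stated figure of more than 150.

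***MP Group P - OLEX*.** Exposed subjects = 90 × (1 − d). Printed rate = true rate × exposed / 90.

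- d = 5%: exposed = 85.5; a true 10% prints as 10% × 85.5/90 = 9.5%.
- d = 15%: exposed = 76.5; a true 10% prints as 10% × 76.5/90 = 8.5%.

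**Whole-number illustration, 8 subjects with an OLEX event.**

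- Total-study table: 8/90 = 8.9%.
- Total-OLEX table with 5 non-entrants: 8/85 = 9.4%.
- Total-OLEX table with 14 non-entrants: 8/76 = 10.5%.

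***MP Total NT 201*.** SES base = 180 + 90 + 90 = 360. Subjects ever given NT 201 = 270 + exposed Group P subjects.

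- d = 5%: 355.5/360 = 0.9875; a true 10% prints as 9.9%.
- d = 15%: 346.5/360 = 0.9625; a true 10% prints as 9.6%.

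**The case against.** The strongest reply is that the SAP leaves this denominator open and does not fix a wrong one. Read literally, the SES is one number for every column, which nobody would program. Once it is read column by column, a programmer could take the SES subjects whom the column describes, namely Group P subjects treated in OLEX, and the total-OLEX rule points that way. SAP Section 1 makes the mock tables the output specification, and their headers are redacted. Section 6 also provides for a footnote where a denominator is not obvious.

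This does not remove the point. The visible text has one rule for each type of period, and the total-study rule has no exception for any column. A footnote discloses the base but does not change it. Redacted mock tables might state another N, but they cannot be presumed to override the written rule. Taking the whole SES as the base would make the mismatch larger.

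Several parts of the reply do stand:

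- The size is assumed. The 15% is planned MP non-completion across all groups, not Group P non-entry to OLEX, and the error is zero if every treated Group P subject is reinjected.
- Delayed entry because lines have not yet returned (protocol Section 6.2) should seldom apply to placebo subjects, so the lower case may be nearer.
- The correct incidence of the same events is already planned in the total-OLEX tables, so no safety result is lost.
- The pooled-column effect is small, and the SAP does not state that column's N separately.

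**Conclusion.** The concern holds, as a minor one. Under the rule as written, with the SES read by MP treatment group, *MP Group P - OLEX* understates incidence by the factor (Group P treated in OLEX / Group P treated in the MP). That factor is 0.95 at 5% non-entry and 0.85 at 15%, assuming 90 treated Group P subjects. The pooled column is understated by about 1% to 4% in relative terms. The 10% rate and the 8 affected subjects are illustrations and come from neither document.

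The scope is every total-study-period TEAE table, including those for related TEAEs. The MP, by-cycle and total-OLEX tables, which report both secondary safety endpoints by period, are correct as planned. The other three total-study columns are also unaffected.

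**What to change.** Add one sentence to the denominator paragraph of SAP Section 6.2. In total-study-period TEAE tables, the denominator for *MP Group P - OLEX* is Group P subjects treated at least once in OLEX, and for *MP Total NT 201* it is all subjects who received at least one NT 201 injection. This extends the treated-in-period principle that the SAP already uses for the cycle and total-OLEX tables.

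At the same time, correct the description of the pooled column. Its label *MP Group P – OLEX, MP* appears to contain a misplaced quotation mark.

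The cost is one sentence, one typographical correction and a small programming change to the column Ns of these tables. No other table changes.

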6.2.1 Primary Safety Endpoints

No primary safety endpoint has been defined.

6.2.2 Secondary Safety Endpoints

Tables displaying incidences of related TEAEs will be provided by system organ class (SOC) and PT for time periods and with table columns as defined at beginning of [Section 6.2](#) above. Related TEAEs in MP and OLEX will also be listed.

CCI

CCI

CCI

CCI

6.4 Special Statistical/Analytical Issues

6.4.1 Discontinuations and Missing Data

Main reasons for premature discontinuation of study will be summarized descriptively. As stated in Section 6.2.3, TEAEs leading to discontinuation will be listed. Discontinued subjects will not be replaced.

For subjects discontinuing the study prematurely and for whom end-of-study visit V17 was documented, efficacy data collected at V17 will be analyzed under the study visit which is closest to the recorded V17 date. This will be based on the assessment date relative to (cycle) baseline, and considering treatment received for each cycle, using the following visit windows.

CCI

For separation of TEAEs from non-TEAEs in case of completely or partly missing start date and time see **CCI** Rules for imputation of start dates and start times of AEs are provided in **CCI** End dates of AEs will not be imputed.

For worst case imputation of missing causal relationship to treatment, intensity or outcome of an AE refer to [Section 6.2](#). Causal relationship to COVID-19 disease will be listed based on observed cases.

If not otherwise specified, all TEAE analyses will be performed on the SES and all further safety analyses on observed cases.

6.4.2 Interim Analyses

Not applicable.

6.4.3 Multiple Comparisons/Multiplicity

The family-wise two-sided type I error level $\alpha = 0.05$ for comparisons of treatment groups U and P on the primary and key secondary endpoints will be controlled by a hierarchical test procedure based on two-sided tests with $\alpha = 0.05$.

The hierarchical procedure for primary analysis ([Section 6.1.1.1](#)) will be performed as described below. First, using the Mantel-Haenszel test of the null hypothesis that the common difference in response rates at Day 30 is zero, Group U versus Group P will be tested for superiority for proportion of GFL-responders, second for proportion of HFL-responders, and third for proportion of LCL-responders. The test procedure will stop once statistical significance could not be reached.

In case statistical significance can be established for all three primary efficacy endpoints, the procedure will proceed to key secondary endpoints ([Section 6.1.2.1](#)): As next steps, Mantel-Haenszel tests for superiority of Group U versus Group P will be conducted for proportion of subjects with a score of 0 (no) or 1 (mild) on MAS at maximum contraction as assessed by the *investigator* at Day 30 for GFL, then HFL and finally LCL anatomical region. Thereafter, Mantel-Haenszel tests for superiority of Group U versus Group P will be conducted for proportion of subjects with a score of 0 (no) or 1 (mild) on MAS at maximum contraction as assessed by the *subject* at Day 30 for GFL, then HFL and finally LCL anatomical region.

Finally, GAIS as assessed by the subject at Day 30 of MP will be tested as described in [Section 6.1.2.1](#).

The hierarchical test procedure will stop once statistical significance could not be reached.

For any other statistical tests on primary or key secondary endpoints (e.g. comparison of treatment groups G&H and P), no type I error adjustment will be performed. The same accounts for any statistical analyses of further secondary and other endpoints.

6.4.4 Examination of Subgroups

Subgroup analyses for the primary efficacy endpoints are specified in [Section 6.1.1.3](#).

Dichotomized endpoints which are based on MAS (assessed by investigator and subject) for GFL/HFL/LCL at rest will be analyzed in subgroups of subjects with baseline score of at least 2 on the corresponding MAS for GFL/HFL/LCL at rest as assessed by both subject and investigator. Since scores at rest are in general lower than scores at maximum contraction, some subjects may have a score of 0 (no) or 1 (mild) at cycle baseline on MAS for GFL/HFL/LCL at rest. These subgroup analyses will be more meaningful and sensitive to treatment effects than analyses of the total FAS as they consider effects in 'symptomatic' subjects, i.e. subjects with 0 (no) or 1 (mild) on corresponding MAS will not be analyzed.

Dichotomized endpoints which are based on IRP assessments on MAS for GFL/HFL/LCL at maximum contraction and at rest will be analyzed in subgroups of subjects with baseline score of at least 2 on the corresponding MAS as assessed by all three raters. These subgroup analyses will be more meaningful and sensitive to treatment effects than analyses of the total FAS as they consider effects in ‘symptomatic’ subjects, i.e. subjects with 0 (no) or 1 (mild) on corresponding MAS will not be analyzed.

6.4.5 Pooling of Sites

No pooling of sites is planned.

6.4.6 Intercurrent Events

ICEs according to ICH E9 (R1) [1] are prespecified for main primary, supplementary primary, and main key secondary efficacy estimands (see Section 5.1.1, [REDACTED] and Section 5.1.2, respectively) and will be addressed by the handling strategies described in [REDACTED]

CCI

In case multiple ICEs with relevance for the same estimand occur for a specific subject, a conservative approach will be adopted for the respective estimand. For example, a composite strategy will be used if this is invoked by at least one of the ICEs relevant for the respective estimand and a treatment policy is used otherwise.

Generally, the above strategies for handling of ICEs will only be applied to estimators for affected estimands. An estimand can only be affected by an ICE if the subject is included in the target

population of the estimand, and only in this case a handling strategy for an identified ICE will be applied.

Likewise, handling strategies for ICEs will not be applied in analyses that are not defined as estimators for any efficacy estimands. This includes, e.g., analyses of primary and key secondary efficacy endpoints on FAS, PPS, observed cases in FAS/PPS and any analyses of further secondary or other efficacy endpoints or any safety or other endpoints.

CCI

CCI

8 References

- [1] ICH E9 (R1): Addendum on Estimands and Sensitivity Analysis in Clinical Trials to the Guideline on Statistical Principles for Clinical Trials, 20 November 2019, adopted by CHMP, 30 January 2020, issued as EMA/CHMP/ICH/436221/2017
